2.8 Final surveys

Just before or after visit 4, patients will again complete the clinically-validated surveys on bladder health (IPSS/AUASI & M-ISI), sexual function (FSFI-6 for women, IIEF-5/SHIM for men), bowel function (CRAD-8), and pelvic pain (FGUPI for women, MGUPI for men). The AUASI and M-ISI surveys are already part of the normal clinical care for these patients at this time point and the F/MGUPI are sometimes also given already. The recruited patients who are in urinary retention with detrusor underactivity will take four surveys (IPSS/AUASI, M-ISI, SQOL-F/M, SF-12v2) at four timepoints in total (enrollment as described in section 2.1, and at approximately 2 weeks, 3 months, and 6 months after stage-1 implant). The 3-month time point for this group will align with the final survey set for all other patients, with this group only completing the IPSS/AUASI and M-ISI once at that point.

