
2.5 Visit 3: Computed Tomography (Aim 3)

As part of their normal clinical care, patients undergo a stage-2 surgery procedure to implant the pulse generator of the implantable neurostimulator. Patients undergo the stage-2 procedure if they have responded positively to the stage-1 procedure, as determined by [name]. Most patients undergoing the stage-1 procedure proceed to the stage-2 surgery, 2-3 weeks after the stage-1 implant. If a study participant does not respond to the stage-1 implanted stimulation lead and they are not having a stage-2 surgery, then they will be removed from the study.

On the same day that participants receive the implanted stimulator in the stage-2 outpatient surgery they will undergo a computed tomography (CT) scan of the pelvis as part of the research study. Again, prior to the CT scan, pre-menopausal women will undergo a urine pregnancy test to detect pregnancy. This test will be similar to visit 1, a research staff member (e.g. study investigator/coordinator/research staff) will administer the test and obtain the results. This test will be covered by the research study. This CT scan will be performed during the same clinical visit as for the stage-2 procedure. If allowed by scheduling and patient preference, the CT scan will be prior to the stage-2 implant, to allow the patient to leave the hospital once they are ready after the implant. Otherwise, the CT scan will be after the stage-2 implant when the patient is ready. This CT scan will be of the pelvis, to determine the final location of the

implanted stimulation electrode, with respect to landmarks like the participant's ischial spine. This CT scan is not part of the patient's normal clinical care for the Interstim implantation, but is the same procedure as used during other patients' care.

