2.7 Visit 4: Stimulation during cystometrogram (Aim 4)

As part of their normal clinical care, patients visit the clinic about 4-5 weeks after their stage-2 surgery. After their clinic visit, patients will undergo an experimental cystometrogram (bladder filling) in a urodynamics suite as part of this research study. This test will occur at the University of Michigan main hospital or a local UMHS clinic, as determined by [name] clinical schedule, in a urology cystometry suite. Prior to the test, pre-menopausal women will undergo a urine pregnancy test to detect pregnancy. This test will be covered by the research study and clinical staff will obtain the results.

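### Section 2.8 aligns the retention subgroup's 3-month survey with visit 4, but the stated intervals put visit 4 at 6–8 weeks after stage 1

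*Protocol*

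**What the plan says.** Four statements in the protocol bear on the timing.

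- **Stage 1 to stage 2** (section 2.5): most patients "proceed to the stage-2 surgery, 2-3 weeks after the stage-1 implant". The background in section 1.1 agrees, with a 2- or 3-week observation period before the pulse generator is implanted.
- **Stage 2 to visit 4** (section 2.7): "patients visit the clinic about 4-5 weeks after their stage-2 surgery". The visit 4 test follows from it: "After their clinic visit, patients will undergo an experimental cystometrogram".
- **Final survey set** (section 2.8): "Just before or after visit 4, patients will again complete the clinically-validated surveys on bladder health", together with the sexual function, bowel and pain surveys.
- **Retention/DUA subgroup** (section 2.8): these patients "will take four surveys (IPSS/AUASI, M-ISI, SQOL-F/M, SF-12v2) at four timepoints in total", namely at enrolment and "at approximately 2 weeks, 3 months, and 6 months after stage-1 implant". The section then states: "The 3-month time point for this group will align with the final survey set for all other patients". It adds that the two bladder surveys are not to be repeated there: "with this group only completing the IPSS/AUASI and M-ISI once at that point".

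The subgroup's clock therefore starts at the stage-1 implant. Its 3-month survey is treated as the same sitting as the visit 4 survey set.

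**The concern.** The interval from stage 1 to visit 4 is the sum of two intervals that the protocol states, and that sum does not come near 3 months. Because IPSS/AUASI and M-ISI are to be completed only once for both purposes, site staff have to choose when that one sitting takes place.

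- **Sitting held at visit 4 (the natural reading).** All four subgroup surveys (IPSS/AUASI, M-ISI, SQOL-F/M, SF-12v2) would carry a 3-month label on data nominally collected at 6–8 weeks. The follow-up points would also be spaced unevenly, with a short first gap and a long second one.
- **Sitting held at a true 3 months.** The subgroup's IPSS/AUASI and M-ISI scores would be set against bladder-excitation and leak-point results obtained several weeks earlier, in the search for relationships described in section 3.2. Other participants' scores would come from around visit 4.

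Only one of these can happen for a given patient. If staff choose differently from patient to patient, one label would cover both timings.

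**Working it through.** **Inputs**

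| Quantity | Value | Source |
|---|---|---|
| Stage 1 to stage 2 | 2–3 weeks (most patients) | Section 2.5 |
| Stage 2 to visit 4 clinic visit | about 4–5 weeks | Section 2.7 |
| Final survey set | just before or after visit 4 | Section 2.8 |
| Subgroup surveys after stage 1 | about 2 weeks, 3 months, 6 months | Section 2.8 |

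Assumptions: the cystometrogram takes place at or close to the clinic visit, and 3 months is read as 12 weeks (3 × 4) or 13 weeks (91 days).

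**Step 1: visit 4 counted from stage 1.** (Stage 1 to stage 2) + (stage 2 to visit 4):
- earliest: 2 + 4 = 6 weeks
- latest: 3 + 5 = 8 weeks

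**Step 2: gap to the 3-month point.** 3 months minus the result of step 1:
- 3 months as 12 weeks: 12 − 8 = 4 to 12 − 6 = 6 weeks
- 3 months as 13 weeks: 13 − 8 = 5 to 13 − 6 = 7 weeks
- overall: 4–7 weeks

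The plan's statement that the two points align is not reproduced under either reading.

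**Step 3: what alignment would require.** With stage 2 at 2–3 weeks, visit 4 would have to fall 12 − 3 = 9 to 13 − 2 = 11 weeks after stage 2. Against the stated 4–5 weeks, that is 9/5 = 1.8 to 11/4 = 2.75 times as long.

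**Step 4: spacing of the subgroup's follow-up surveys.**

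| Middle survey | 2 weeks to middle point | Middle point to 6 months |
|---|---|---|
| 3 and 6 months as 12 and 24 weeks | 12 − 2 = 10 | 24 − 12 = 12 |
| 3 and 6 months as 13 and 26 weeks | 13 − 2 = 11 | 26 − 13 = 13 |
| Held at visit 4 (6–8 weeks) | 6 − 2 = 4 to 8 − 2 = 6 | 24 − 8 = 16 to 26 − 6 = 20 |

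A nearly even series of 10–11 then 12–13 weeks becomes 4–6 then 16–20 weeks.

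**Step 5: how many patients.** The protocol does not state the subgroup's size. The nearest figure is the target in section 5 of at least 8 DUA patients among 40, or 8/40 = 20%. The subgroup is narrower, since it also requires retention and a failed prior treatment.

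**The case against.** The strongest reply is that the timeline itself is missing from the copy reviewed. Section 2.9 refers to Figure 4 for each participant's standard timeline, and that figure may place visit 4 later. The 6–8 weeks is a sum and is stated nowhere. The 2–3 weeks applies to most patients, and the 4–5 weeks dates a routine clinic visit and is itself approximate.

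There are also reasons why visit 4 could slip. It uses stimulation settings from a patient-specific model that needs the imaging (sections 2.6 and 2.7). Some patients with an old implant that is not MRI-compatible have their MRI late (section 2.2). Failed S3 neuromodulation is one route into this subgroup (section 2.1), so that may apply to some of its members. Section 4 allows surgeries to be staggered or delayed. The loose figure could therefore be the one in section 2.7 and not the 3 months.

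This limits what can be claimed. It does not predict when visits will actually take place, and it leaves open which figure was intended. It does not remove the contradiction: none of these passages states a visit 4 at 3 months, and section 4 ties every study part except the MRI to standard clinical visits. Delaying surgery does not by itself lengthen the time from stage 1 to visit 4. A figure with other intervals would still leave the three sections in conflict as written.

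The objection to the consequences partly stands. The protocol describes no analysis that depends on equal spacing, and the survey comparison in section 3.2 is exploratory. Section 2.8 says AUASI and M-ISI are already routine at the visit 4 time point, so scores from near visit 4 should exist even if the subgroup is surveyed at a true 3 months. That softens the mispairing. It does not settle which sitting the protocol means or how the other two surveys should be labelled.

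**Conclusion.** The concern holds as a contradiction within the protocol's text. Sections 2.5 and 2.7 place visit 4 nominally 6–8 weeks after stage 1, and section 2.8 equates it with a point 12–13 weeks after stage 1. The gap is 4–7 weeks, or 5–7 weeks if 3 months is read only as 13 weeks.

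Severity is minor. The effect is confined to four surveys at one of four time points in a small subgroup of unstated size. Neither the primary outcome nor the listed secondary outcomes use the surveys. The conclusion takes the stated intervals at face value and places the cystometrogram at or near the clinic visit. It was reached without sight of Figure 4.

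**What to change.** Reconcile sections 2.5, 2.7 and 2.8 with Figure 4, then adopt one of two wordings in section 2.8.

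1. **If the survey is meant to be taken at visit 4:** describe the subgroup's middle survey as taking place at visit 4 and give its nominal weeks since stage 1 in place of 3 months. This is the simplest change and costs one line of wording.
2. **If a true 3-month survey is meant:** remove the statements that it aligns with the final set and that IPSS/AUASI and M-ISI are completed once. Use the routine AUASI and M-ISI from around visit 4 for the section 3.2 comparison. Collect the subgroup's four 3-month surveys separately by phone, mail or online, which section 2.1 already allows. This costs one amendment line and one further completion of two short questionnaires by the subgroup, with no added visit.

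The choice depends on what the investigators intended, which the text does not settle.

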2.9 Patient timeline

Figure 4 gives a summary of the standard timeline for each study participant.

3. Study Statistics and Data Analysis Plan

3.1 Sample size

The target population size (N=40) was selected based on [name] clinical practice and direct input from the funding agency (NIH SPARC). We seek to have 20 patients complete all parts of this study and yield data. Due to patient heterogeneity (e.g. prior surgical procedures that limit effects of neural stimulation; implanted hip replacements that obscure MRI data) and drop-outs among enrolled patients, we anticipate that approximately half of enrolled participants will complete all study steps and yield usable data. This study size is within the range of sample sizes used in prior pelvic floor / pudendal nerve anatomy mapping studies with cadavers (N=7 [23], 13 [55], 28 [56], 43 [57]). To our knowledge, no studies have performed pudendal mapping with MR imaging data. Additionally, this sample size is comparable to prior human subject studies stimulating the pudendal nerve or its branches (N=10 pudendal implant after sacral implant [58], N=12 cutaneous genital nerve [59], N=21 percutaneous genital nerve [60], N=30 pudendal versus sacral implant [26]).

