1.4 Primary Outcomes

The primary outcome measure in this study are evoked bladder contractions of at least 20 centimeters of water (cmH₂O) during the stage-4 test in at least 50% of participants.

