At two or more time points within a cystometrogram, the urethral leak point pressure (ULPP) will be measured during Valsalva and/or forceful coughing. This will occur after infusing saline into the bladder to an intermediate volume(s) below the sensation of fullness and then pausing. Urethral leakage may not be observed; however, urethral pressures will be recorded and compared to pressures during pudendal nerve stimulation. If leakage is observed, an equal amount of saline may then be reinfused. Pudendal nerve stimulation will be turned on to a stimulation paradigm for maximum urethral sphincter activation at a comfortable level, for a maximum of a 60-second pulse train while the ULPP measurement is repeated using Valsalva and/or forceful coughing. The saline infusion will then be resumed until the participant perceives fullness and then will be stopped. Leak point pressure will again be assessed without and then with pudendal nerve stimulation as before. Each assessment of leak point pressure may be performed with stimulation on and then repeated with stimulation off, or with

stimulation off and then repeated with stimulation on. The ULPP testing may be repeated at the Investigator's discretion and participant's agreement. The ULPP measurements and stimulation-driven voiding experiments may be integrated in a fill sequence, such that both assessments may be completed at the same fullness sensation bladder volumes, using the respective stimulation parameters for each assessment.

[figure not shown]
All stimulation parameters used will be within the normal hard-coded limits of the IPG. We will not be testing new paradigms that the IPG is not capable of performing. We may vary the combination of lead contacts that are active, the pulse width of applied stimulation (i.e. duration of each pulse), the frequency of applied pulses (i.e. cycles per second), and the amplitude (i.e. volts or milliamps) of the applied stimulation. If any stimulation paradigms are perceived as uncomfortable by the participant, they will be stopped and alternate paradigms will be attempted. Once testing is completed, the IPG will be returned to the clinically-determined stimulation settings for the patient.

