3.2.2 Bladder excitation

The primary metric of successful bladder excitation will be a target evoked bladder contraction of at least 20 cmH₂O during the visit 4 cystometrogram in at least 50% of participants. Additionally, any stimulation-driven or participant-driven voiding efficiency will be calculated as

[volume voided] / [volume voided + residual measured still in bladder].

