3.2.3 Leak Point Pressure

The ULPP will be determined as the maximum urethra pressure during any Valsalva and forceful coughing events from the urethra catheter sensors. The ULPP during pudendal nerve stimulation will be compared to the ULPP without stimulation at each volume level tested.

4. Study Recruitment

[name] will recruit patients in her clinical practice that fail conservative treatments for relevant bladder symptoms and are being considered for a pudendal nerve implant. Generally, these patients are very willing to help, as they have failed a series of prior conservative treatments and they know the pudendal implant is an off-label use. We will augment this recruitment by asking other U-M Urology clinicians to refer patients of theirs who may be candidates. Additionally, we will recruit patients from [name] practice and other Urology clinicians who have failed treatment with an implanted Interstim neurostimulator at the sacral nerve. Either [name] will perform the subject recruitment or she will introduce the patient to the study coordinator, who will then discuss the study with the patient and perform recruitment. Patient information will not be shared outside of direct clinical conversations or inquiries by the study coordinator.

As has been reported previously, patients who fail the traditional sacral nerve Interstim implant often respond positively to pudendal nerve implants [26], [61]. [name] will recruit sacral-nerve implanted patients who did not achieve clinical success to have a replacement implant at the pudendal nerve. Failed-sacral patients will be broadly recruited across clinicians within the Neurourology and Pelvic Reconstructive Surgery section at the University of Michigan Health System, which includes six Urologists who regularly see these types of patients and implant Interstim devices. Any patients not initially under [name] care who are interested in this study will be referred to her for subsequent care for receiving the IPG as well as any participation in this study. Additionally, we will also look for patients with urinary retention with detrusor underactivity and have failed bladder outlet surgery, S3 neuromodulation or a PTNS trial. These patients will be identified and referred to the study by [name] and her clinic.

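### Does naming limited stimulation effect as a source of unusable data in section 3.1 bias the 50% primary result upwards?

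*Protocol*

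**What the plan says.** Section 3.1 sets enrolment at 40 and seeks 20 people who finish every part and give data. It expects that "approximately half of enrolled participants will complete all study steps and yield usable data", and attributes the shortfall to drop-out and to patient heterogeneity, with two examples: "prior surgical procedures that limit effects of neural stimulation; implanted hip replacements that obscure MRI data".

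The primary outcome is an evoked bladder contraction of at least 20 cmH2O. Sections 1.4 and 3.2 place it "during the stage-4 test in at least 50% of participants", and section 3.2.2 places it "during the visit 4 cystometrogram in at least 50% of participants". None of the three says which participants form the base of the percentage, and none mentions usable data.

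Section 2.5 says "Most patients undergoing the stage-1 procedure proceed to the stage-2 surgery". It also says that a participant who does not respond to the stage-1 lead and is not having stage-2 surgery is removed from the study.

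Section 4 recruits people with earlier procedures. It states that "patients who fail the traditional sacral nerve Interstim implant often respond positively to pudendal nerve implants", and adds that "we will also look for patients with urinary retention with detrusor underactivity and have failed bladder outlet surgery", S3 neuromodulation or a PTNS trial.

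**The concern.** The two examples in section 3.1 differ in kind. A hip replacement that obscures the MRI is a measurement problem with no built-in link to the bladder response. Prior surgery that weakens stimulation bears directly on what the primary outcome measures. Someone stimulated at visit 4 who does not reach 20 cmH2O has a valid negative result, and calling that result unusable would select on the outcome.

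The people concerned may well reach visit 4. Section 4 recruits patients after failed sacral implants and failed outlet surgery, and most stage-1 patients go on to stage 2. A good clinical response at stage 1 is also not the same as a 20 cmH2O contraction at visit 4. With the target at exactly 50% of about 20 people, one tested failure set aside can turn a missed target into a met one.

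**Working it through.** **The plan's own figure.** Section 3.1 wants 20 with usable data and expects to lose half: 20 / (1 − 0.5) = 40. This reproduces the stated enrolment. No null rate, alpha or power is stated, so there is nothing further to reproduce.

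**Size of the effect if failures were set aside.** Inputs: 20 usable participants (section 3.1) and a 50% target (sections 1.4, 3.2, 3.2.2), so 10 successes meet it. Assumption: m further people are tested at visit 4, do not reach 20 cmH2O and are left out. The protocol gives no m; 1, 2 and 4 are illustrations.

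- Observed proportion: 10/20 = 50%.
- Proportion with everyone tested counted: 10/(20 + m).
- Successes needed with everyone counted: (20 + m)/2, rounded up.
- With X ~ Binomial(20 + m, p), the chance of declaring the target met is P(X ≥ 10) on the usable set and P(X ≥ (20 + m)/2, rounded up) on all tested. The true rate p is also an assumption.

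| m | 10/(20 + m) | Needed | p = 40%: usable v all | p = 50%: usable v all | p = 60%: usable v all |
|---|---|---|---|---|---|
| 0 | 50.0% | 10 | 24.5% v 24.5% | 58.8% v 58.8% | 87.2% v 87.2% |
| 1 | 47.6% | 11 | 31% v 17% | 67% v 50% | 92% v 83% |
| 2 | 45.5% | 11 | 38% v 23% | 74% v 58% | 95% v 88% |
| 4 | 41.7% | 12 | 51% v 21% | 85% v 58% | 98% v 89% |

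The direction is certain when there is at least one success: leaving out a failure raises the proportion. Part of the m = 1 contrast is rounding, because 11/21 is 52.4%, a stricter bar than 50%. With m = 0 there is no difference.

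**Does the protocol plan such an exclusion?** Four readings of the text bear on this.

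1. Section 3.1 explains why 40 are enrolled to obtain about 20. It is a forecast, and no sentence in it says whom the 50% is computed on.
2. The forecast covers a joint condition: completing all steps and yielding usable data. The protocol does not say which half of that condition limited effect belongs to. Section 2.5 supplies a route through non-completion: stage-1 non-response without stage-2 surgery leads to removal before visit 4. That is the only removal for poor response in the protocol, and no visit 4 result exists to discard.
3. Usable data covers every aim, not only the bladder outcome. The Selectivity Index in section 3.2.1 divides by the sum of the evoked responses, so it becomes unstable as these approach zero. Section 2.6 validates the model against stage-1 recordings. Limited effect can therefore spoil mapping and modelling data without touching the validity of a visit 4 failure.
4. Section 3.1 does not say which prior procedures it means. Section 4 reports that failed-sacral patients often do well with pudendal implants, which does not mark them as the limited-effect group.

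**The case for a change.** The best case for a change is that this goes beyond missing detail. The protocol's statistics section contains a phrase that treats a cause of primary-outcome failure as a reason for unusable data, and no sentence states that a tested person without a contraction counts as a failure. A later analysis plan that took its analysis set from the 20 usable participants would carry the problem forward. Clarifying this before results are known would cost a few words.

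Part of this stands. The wording in section 3.1 is loose, the word participants is undefined, and the arithmetic shows that a wrong choice would matter near the threshold. It does not establish that the protocol makes that choice. The bias needs a link from the enrolment forecast to the primary denominator, and no section supplies one. Without it, what remains is a request to define the analysis population, which a protocol commonly leaves to the statistical analysis plan. That plan is not at hand.

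**Conclusion.** No change to the plan is needed. Followed as written, the primary proportion is taken over participants in the visit 4 test, and a person given bladder-directed stimulation there without a contraction of at least 20 cmH2O is a failure whatever the surgical history. A competent analyst would also not count someone who received only the "stimulation paradigm for maximum urethral sphincter activation at a comfortable level" of section 2.7, since that paradigm targets the urethral sphincter and not the bladder.

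The possible upward shift is conditional on the usable set becoming the denominator. Its size rests wholly on an unknown number of excluded failures: none with m = 0, and from 50% to 41.7% at the threshold with m = 4. The conclusion assumes that the analysis plan does not take the usable set of section 3.1 as the base of the 50%; nothing in the protocol says that it should.
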